There are no costs to research participants or their insurance companies (there are no clinical visits or billable procedures.) – *You may delete the rest of the section.*

1. Describe what costs research participants will be responsible for as a result of their participation in the research, including but not limited to: clinical services required by the protocol deemed billable to insurance, transportation to study visits, parking, costs of drugs, cost of therapy, lost broken or stolen devices, etc.
2. Explain who will be responsible for payment of provided services in the event of insurance denials.
3. List what procedures, drugs, devices, supplies will be paid by the study sponsor or covered by other funding. List the other funding source.

Research Participant Compensation

There is no compensation for research participants – *please leave rest of this section blank*
 There is compensation for research participants.

Describe the schedule, payment method, and payment total of any incentives or compensation that research participants will receive for participation in the research (e.g., gift cards or cash with amount, t-shirts, devices, bags, swag, etc.)

Gift card incentives will be increased over time: \$20 at T1, \$25 at T2, and \$30 at T3. Carers will also receive a \$20 gift card for the face-to-face intervention session and \$5 gift cards for each week (up to 4 weeks/ \$20) of completion of the workbook, distributed after the 28-day intervention time frame. Thus, each subject may receive up to \$115 in gift card compensation for completion of all study activities.

There will be reimbursement for research participants.
Describe the schedule, payment method, and payment total of any reimbursement that research participants will receive for participation in the research (e.g., gift cards or cash with amount, etc.)

If someone takes a bus or drives to CWRU or other community location to meet a research team member for T1, T2, T3, or an intervention meeting, we will reimburse that individual a 2-trip bus pass or parking voucher as appropriate.

Compensation for Research Related Injury

Describe who will pay for the costs of medical treatment and/or compensation in the event of a research related injury:

- Funding agency is providing some/all payment for injury
- Funding agency is providing no payment for injury
- N/A

Provisions to Monitor the Data to Ensure the Safety of Research Participants

1. Describe how often the data will be monitored for completeness, accuracy and adherence to the protocol.
2. Indicate if there will be a Data and Safety Monitoring Board or Committee:
 - There will not be a formal Data and Safety Monitoring Board/Committee.
 - There will be a formal Data and Safety Monitoring Board/Committee.

Provide information about the DSMB/C including the contact information of the committee member(s) (as applicable); whether it is independent from the study sponsor; how often it meets; the type of data that will be used; written reports, etc.

A Safety Monitoring Committee (SMC) has been formed as the monitoring entity for this grant. The SMC is independent from the study sponsor and consists of:

- [name] , SMC chair, who serves as the Associate Dean for Research and is Associate Professor, Frances Payne Bolton School of Nursing, CWRU
[contact]
- [name], Assistant Dean for Research, and Professor, Frances Payne Bolton School of Nursing, CWRU
[contact]
- [name], Professor of Psychiatry from the CWRU School of Medicine, [contact]
- Study team members will include [name], PI, and [name], statistician [contact]

1. Monitoring Study Safety

- a) Monitoring schedule - Twice per year throughout the project, the SMC will review data on the study regarding study safety. For example, the SMC will review any occurrences of carer emotional distress that required intervention by data collector or interventionist as well as those requiring referral and follow-up and instances where carers withdrew from the study.

HRP- 503SBER	TEMPLATE: SBER Protocol		
Approved:	01/2019	Prior Version:	05/2018

b) Audits for compliance with IRB requirements – Random internal audits of 10% of the files will be done twice annually to insure the approved IRB protocol is being followed. The SMC will review recruitment procedures, compliance with meeting the inclusion/exclusion criteria, consistency with random assignment process to the treatment conditions, provision of interventions within timeframe defined within the protocol, and scheduling of data collection sessions as outlined within the protocol.

c) Conformance with informed consent requirements – Random internal audits will be conducted twice per year to verify that informed consent requirements are being met. For example, the SMC will review 10% of the consent forms for signatures and dates, make sure all consent forms are accounted for and stored in locked files and that the correct form is being used. Data collectors will be asked to describe the consent process quarterly to re-assess their knowledge of this process quarterly and review / retraining will be done as needed.

d) Verification of source documents – This study does not involve printed or written documents; data will be collected through electronic data capture using REDcap software and then downloaded directly into SPSSPC files. Heart rate variability data will be downloaded from the assessment device and transcribed into the SPSSPC files. These sources will not include any data that would be personally identifiable.

The SMC will review 1) all causes of mortality (e.g., carer death); 2) issues with participation (e.g., numbers and reasons for withdrawing from the study or refusing interventions, etc.) as well as recruitment refusal (percent and reasons) and subject attrition (percent and reasons); 3) missing data (including whether there are systematic patterns or whether data are missing at random); and 4) errors in data entry (which are expected to be minimal given the use of software for data collection with direct download into SPSS). In addition, differential attrition from the intervention groups (including the control and usual care groups, and the groups assigned to intervention based on need or personal preferences) will be monitored.

If concerns or problems are identified by the SMC, they will be reported to the IRB and NINR/NIH via email by [name] and [name], respectively, within 3 business days after they are identified. If there are recommendations made by the SMC, the action plan for response or notice of any actions taken by the IRB regarding the research and any responses to those actions will be provided to NINR Officials within 2 weeks.

e) Investigator compliance – Compliance of the investigators and all research team members who will have access to the data will be monitored annually. All research team members will be CREC certified; the CWRU intranet hosts a website where verification of compliance with continuing education for all investigators and team members can be evaluated.

2.) Reviewing and Reporting Adverse Events/unanticipated problems

HRP-503SBER	TEMPLATE: SBER Protocol		
Approved:	01/2019	Prior Version:	05/2018

1. Event identification

At the onset and for the duration of the study, all research staff and investigators will have instructional review of the nature and types of unanticipated and adverse events as described by the CWRU IRB. Potential risks for this study may include carer distress and breach of confidentiality (as described above). Carer distress may be identified by the data collector (during data collection) or the interventionist (during the interventions or phone follow-up). Breach of confidentiality may be identified by any research team member.

2. Reviewing and reporting

As they occur, all unanticipated events and adverse events will immediately be reported to [name] (PI) who will report them to the IRB according the CWRU IRB protocol reporting procedures for both serious and non-serious adverse events and unanticipated problem reporting. These will be summarized in the semi-annual reports to the SMC. Annual progress reports to the CWRU IRB and NINR/NIH will include a summary of the SMC's activities and findings as well as any adverse events regarding human subjects. Program Officials at NINR will be informed in a timely manner (3 business days) of unanticipated problems (e.g., a data breach) or unexpected serious adverse events that may be related to the study protocol or IRB-approved revisions to the study protocol that indicate a change in risk for participants. All adverse events and protocol deviations will be reviewed with the staff involved within 3 business days. Factors leading up to the event or deviation will be discussed and strategies for preventing recurrence will be developed and implemented immediately.

Community-Based Participatory Research

- This is not a community-based participatory research project – please leave the rest of this section blank
- This is a community-based participatory research project
Describe the involvement of the community in the design and conduct of the research.

Note: Community based research is research that is conducted as an equal partnership between academic investigators and members of a community. In Community Based Participatory Research (CBPR) projects, the community participates fully in all aspects of the research process.

MULTI-SITE RESEARCH (when UH or CWRU is the IRB of Record)

Does this project have multiple sites?

- Yes
- No – please leave the rest of this section blank

Non-Local Site Information for Multi-Site Studies

If this is a multi-site study where you are the lead investigator, list the following information for each relying site:

HRP-503SBER	TEMPLATE: SBER Protocol		
Approved:	01/2019	Prior Version:	05/2018

1. Name of site:
2. PI of relying site:
3. Name of IRB contact:
4. Phone number of IRB contact:
5. Email address of IRB contact:

Non-Local Recruitment Methods for Multi-Site Studies

If this is a multi-site study and research participants will be recruited by methods not under the control of the local site (e.g. call centers, national advertisements) describe those methods.

Local recruitment methods are described above.

1. *Describe when, where, and how potential research participants will be recruited.*
2. *Describe the methods that will be used to identify potential research participants.*
3. *Describe the materials that will be used to recruit research participants.*

Multi-Site Research Communication Plan (when you are the lead investigator)

If this is a multi-site study where you are the lead investigator, describe the processes to ensure communication among sites including:

- All sites will have the most current version of the protocol, consent document, and HIPAA authorization*
- All required approvals (initial, continuing review and modifications) have been obtained at each site (including approval by the site's IRB of record)*
- All modifications have been communicated to sites, and approved (including approval of the site's IRB of record) before the modification is implemented*
- All engaged participating sites will safeguard data, including secure transmission of data, as required by local information security policies*
- All engaged participating sites will safeguard data, including secure transmission of data, as required by local information security policies*
- All local site investigators conduct the study in accordance with applicable federal regulations and local laws*
- All non-compliance with the study protocol or applicable requirements will be reported in accordance with local policy*

If this is a multi-site study where you are the lead investigator, describe the method for communicating to engaged participant sites the following:

1. *Problems:*
2. *Interim results:*
3. *The closure of the study:*

Additional Information

If you have any additional information regarding your study not covered in the template, please include it here.

HRP- 503SBER	TEMPLATE: SBER Protocol		
Approved:	01/2019	Prior Version:	05/2018

Study Information stored in Box.com:

- Screening & Enrollment Log (screening ID, name, phone number and/or email, staff notes regarding eligibility status of individual, Study ID, Screen date, Informed Consent date, T1 date, Intervention date, T2 date, T3 date, End-of-Study date)
- Uploaded HRV data
- Copy of current informed consent form, and current protocol
- Project Manager will keep REDCap back-up files (updated monthly) in Box.com. Files will be in SPSS format, and these separate files will be accessible only to the Project Manager and Data Coordinator.

Study Information stored in REDCap:

- Screening form (criteria questions answered, verbal study consent, and consent for future research), Contact Form (name, address, phone number, preferred contact methods and times), eConsent (signed copies saved in File Repository, automatically includes IP address), Enrollment form confirming enrollment date, consent form signed digitally or paper copy; Randomization form with intervention assignment and-End-of-Study forms. Study team members, depending on role, have access to different forms.
- Interventions and Weekly meetings (different staff, depending on role, have access to different forms): Intervention tracking (date of intervention, weekly follow-up contact).
- Surveys Project: All study instruments

Stored on Network drives:

- No PHI is stored on network drives
- Internal study files such as grant proposal, IRB folder, marketing materials.

References

1. Alzheimer's Association. (2016). Alzheimer's disease facts and figures. *Alzheimer's & Dementia*, 12(4), 22. <http://dx.doi.org/10.1016/j.jalz.2016.03.001>
2. Gaugler, J.E., & Teaster, P. (2006). The family caregiving career for community-based long-term care practice and policy. *Journal of Aging & Social Policy*, 18(3/4), 2006, 141-154. doi: 10.1300/J031v18n03_10

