Based on the foregoing review, this study will: 1) include a sample of dementia carers that include caregivers (in-home), care partners (with a facility), and caretakers (bereaved) who have recently (within six months) transitioned into a new phase of their caregiving career; 2) examine the effects of two self- management interventions delivered to carers based on their need (cut score) or preference in comparison with an attention control condition; 3) explore differences in carers at the three phases of the caregiving career on caregiver responses to their recent transition and health outcomes over time; and 4) control for the effects of number of months in carer role, dementia symptom severity, and caregiving demands. As such, this will be the first study to investigate self-management interventions across all three phases of the caregiving career of dementia carers.

Inclusion and Exclusion Criteria

Directions: Describe how individuals will be screened for eligibility. Using the tables below, describe the inclusion and exclusion criteria that will define who will be included and excluded in your final study sample.

Inclusion

1. At least 18 years old
2. Have a living family member, or a recently deceased family member diagnosed with Alzheimer's disease or another dementia
3. Identify self as a primary caregiver
4. In-home **Caregivers**: must be currently providing a minimum of 4 hours per day of supervision/direct care, and have entered that role within the past six twelve months;

Care partners whose family member moved into a nursing or assisted living

HRP-503SBER	TEMPLATE: SBER Protocol		
Approved:	01/2019	Prior Version:	05/2018

facility within the past ~~six~~ twelve months, and must report visiting their care recipient at least once per week (or have similar involvement with COVID-19 restrictions).

Caretakers (i.e. bereaved) whose family member is deceased within the past ~~six~~ twelve months, and are persons with direct oversight of the deceased person's belongings, estate, finances, etc., and/or while their family member was alive, did they consider yourself a primary caregiver (whether care recipient was at home or in a facility).

5. Be capable of performing informed consent and participating in study procedures

Exclusion

1. Does not have family member with Alzheimer's disease or another dementia

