2. Has not cared for a living family member with dementia within the last ~~six~~ twelve months, or the family member has been deceased for more than ~~six~~ twelve months
3. Has knowledge of another family member in the same household enrolled in the study
4. Currently pregnant
5. Has a pacemaker
6. Lives outside of the study area

Number of Research Participants

Directions: Indicate the target number of research participants to be accrued locally, and, if this is a multi-site study, indicate the total number of research participants to be accrued across all sites.

Based on previous research by the PI and Co-Is, we conservatively estimate that ~20% of carers may not meet eligibility criteria. Thus, we will screen ~~~375 participants~~ 600 individuals to obtain the desired sample of size of ~~300-350~~ 350.

Special/Vulnerable Populations

1. *Indicate specifically if you will include each of the following special populations by checking the appropriate box:*

- Adults unable to consent**
- Minors (infants, children, teenagers)**
 - Wards of the state
 - Foster Children
- Pregnant Women**
- Neonates**
- Neonates of Uncertain Viability**
- Employees of CWRU or UHHS**
- Prisoners**
- Illiterate Individuals**

HRP- 503SBER	TEMPLATE: SBER Protocol		
Approved:	01/2019	Prior Version:	05/2018

- Non-English Speaking**
- University Students**
- None**

2. If the research involves individuals that are included in a special/vulnerable population, describe the additional safeguards included to protect the rights and welfare of the individuals for each population indicated.

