- We will contact dementia care day programs and care facilities, and private physicians' offices who agree (with a signed Letter of Cooperation) to provide us with access for posting / distributing information about the study. Agency personnel may assist us in identifying potential study participants who meet the inclusion criteria. We may also recruit through these agencies with digital or printed ads in newsletters.
- We will collaborate with community agencies (e.g. senior centers) to conduct short presentations to interested audiences. Time permitting, we will utilize the NIH Recruiting Older Adults into Research (ROAR) open-source short form PowerPoint presentation (<https://www.nia.nih.gov/health/recruiting-older-adults-research-roar-toolkit>) in addition to presenting information about our study (e.g. distributing flyers).
- Health fairs and other community events.
- We will recruit via the internet using social media sites (e.g. Twitter, Facebook, Instagram, and other online sources). We will also utilize paid digital and print advertising in local newspapers and other appropriate media outlets, including the use of advertorials and/or posted ads.
- Digital recruitment may include a link to a secure REDCap form so that people may leave their contact information for us to follow-up with. The form will include a brief description of the study.
- Most potential study participants will be those who see a posted advertisement or receive a flyer describing the study from one of agencies, centers, dementia care facilities, offices, etc., where we have permission to post / distribute information about the study. Contact information for the research office will be included on the flyers, postcards, and other advertisements. Potential study participants will contact the research office for screening by a research team member to ensure he/she meets the eligibility criteria. If eligible, the research team member will confirm their name, contact information (phone and/or email), address, and time / best method for the research team to contact them, and proceed with the consent process and scheduling the first data collection session.
- Finally, we will use snowball recruitment by asking study participants to refer others like them to the study.

3. Describe the source (e.g., from what department, EMR, etc.) of the research participants.

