Potential study participants will be recruited through flyer postings, health fairs and other community events, print and e-newsletters (e.g. CASE Daily), community bulletin boards (both physical and virtual, e.g. Case Campus Groups), listservs, local magazines and newspapers, volunteer recruitment sites such as ResearchMatch.com and Alzheimer's Association TrialMatch, both public and private advocacy agencies, care facilities, support groups, community health centers, and private physician offices in Cuyahoga and 6 adjacent other approved counties in Northeastern Ohio.

To enhance recruitment of bereaved caretakers, we will also work with a large mortuary firm in Cleveland, known for its efforts to provide post-funeral support to bereaved families, as well as other mortuaries that serve the study area. We will also work with funeral homes, regional hospice agencies, bereavement support groups, and online obituary and memorial sites (e.g. Cleveland.com, legacy.com). Letters of Cooperation will be obtained from these agencies.

4. Describe the methods that will be used to **identify** potential research participants.

When a person contacts the study to be screened, they will receive a screening ID in the Screening & Enrollment log. Contact information will then be collected including date of initial contact, name, telephone number(s), email address(es), and mailing address on all individuals screened will be collected for our screening log; this information will be stored in REDCap and a password-protected computer file (Box.com).

The project manager or other trained research staff will screen by phone to ensure that caregivers meet all eligibility criteria. We will also be collecting demographic information (gender, race, ethnicity, etc.). ~~They will also be asked if they would like to be contacted regarding future research opportunities that may be of interest to them.~~ All screening question documentation will be kept in a screening form on REDCap along with screening ID.

If the screenee is eligible:

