INTERVENTION: Within two weeks of the first data collection session (including study scales and HRV data collection), carers within each of the three caregiving phases (caregivers, care partners, and caretakers) will be randomly assigned using a computer program to one of three treatment groups: 1) Self-management (SM) need, 2) Self-management (SM) preference, or 3) attention control. The SM-need group will receive a self-management intervention tailored to meet their need for resourcefulness training (RT) or biofeedback (BF) as

HRP- 503SBER	TEMPLATE: SBER Protocol		
Approved:	01/2019	Prior Version:	05/2018

determined by whichever baseline cut score is lower, the Resourcefulness Scale or the SDNN parameter for age and gender. Carers randomly assigned to the SM-preference will choose to do RT or BF according to their personal preference. However, we will use minimization methods for group assignment to ensure equivalent representation across the three treatment groups, and factors likely to affect variables of interest, including carer age, gender, and race/ethnicity, in order to insure demographic similarity.

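### Exclusion 3 stops a second relative only if the two share a household and the candidate knows of the enrolment, so two carers of one person can enter different arms

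*Combined protocol and SAP*

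**What the plan says.** Exclusion 3, under Inclusion and Exclusion Criteria, bars a candidate who "Has knowledge of another family member in the same household enrolled in the study". No other text limits enrolment to one carer per care recipient or per family.

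The inclusion criteria do not do it indirectly. Inclusion 3 is a self-declaration: "Identify self as a primary caregiver". In-home caregivers "must be currently providing a minimum of 4 hours per day of supervision/direct care". Care partners "must report visiting their care recipient at least once per week". Caretakers qualify if they "are persons with direct oversight of the deceased person's belongings, estate, finances, etc., and/or while their family member was alive" regarded themselves as the primary carer.

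Recruitment Methods includes referral by participants: "Finally, we will use snowball recruitment by asking study participants to refer others like them to the study". It also uses care facilities, hospices, funeral homes and obituary sites; for instance, "To enhance recruitment of bereaved caretakers, we will also work with a large mortuary firm in Cleveland". Screening is by telephone against the criteria, and no staff check for enrolled relatives is described.

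Under Study Design/Procedures, "carers within each of the three caregiving phases (caregivers, care partners, and caretakers) will be randomly assigned using a computer program" to one of three groups, with minimisation on factors that include age, gender and race/ethnicity. Family is not named among them. The Data Analysis Plan uses RMANOVA and RMANCOVA and describes no family term.

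**The concern.** The rule is attached to the carer's household and to what the carer happens to know. The unit that matters is the care recipient. Placement in a facility or a death is an event in the care recipient's life, so it opens the eligibility window for every involved relative at once, wherever they live. In-home care can also be shared between relatives with separate homes, since no criterion requires the carer to live with the person cared for. Even two people in one household pass if the second is unaware of the first, and the privacy section says that participants' names are not shared with other participants.

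Once both are enrolled, nothing keeps them in the same arm. The brochure, workbook, RESOURCE card and hand-held device are portable. A control carer who learns the skills from a relative moves the control arm towards the active arms. If family links are not recorded, this cannot be detected afterwards. The same care recipient also contributes twice to the analysis.

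**Working it through.** There is no figure in the plan to reproduce: it gives no power calculation, share of related participants, intraclass correlation (ICC) or effect size. The check is therefore a reading of the criteria, followed by an illustration.

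**Can two relatives both qualify?** Two people can each give four hours of care a day, each visit weekly, or each have regarded themselves as primary carer of someone now deceased. The caretaker criterion is and/or, so only one of them needs to hold the estate. The gap exists in all three phases.

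**Where would a pair land?** Assume three equal arms and independent allocation; minimisation could shift these values.
- Different arms: 1 − 3 × (1/3)² = 2/3.
- One in an active arm, the other in control: 2 × 1/3 × 2/3 = 4/9.

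**Contamination, Aim 1.** Inputs: target 350, so 350/3 ≈ 116.7 per arm. Assumptions: a comparison of one active arm with control, two-sided 5%, and the standardised effect that gives 80% power: (1.960 + 0.842) × √(2/116.7) = 0.367. If a share f of carers is in same-recipient pairs, a share c = f × 2/3 of control carers has a relative in an active arm. If all of them take up the content fully, the effect shrinks to 0.367 × (1 − c), and restoring 80% power needs 350/(1 − c)².

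| f | c | exposed controls of 116.7 | effect | power | total to restore 80% |
|---|---|---|---|---|---|
| 2% | 1.3% | 1.6 | 0.362 | 78.9% | 360 |
| 5% | 3.3% | 3.9 | 0.355 | 77.3% | 375 |
| 10% | 6.7% | 7.8 | 0.342 | 74.4% | 402 |

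**Non-independence, Aim 1.** For a comparison of two arms, a pair falls in the same one of those arms with probability 2 × 1/9 = 2/9, which inflates the variance. It is split between them with probability 2/9, which reduces the variance by the same amount. The two cancel. A simulation with 10% of carers in pairs and an ICC of 0.5 gave a variance ratio of 0.99.

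**Non-independence, Aim 2.** Relatives of one person will usually be in the same phase, so there is no cancelling. The design effect is 1 + f × ICC.
- f = 2%, ICC 0.1: 1.002, effective sample 349, power 79.9%.
- f = 10%, ICC 0.5: 1.05, effective sample 350/1.05 = 333, power 78.1%.

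These assume equal phase groups and the same 0.367 effect.

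**The case against.** The strongest reply is that pairs should be uncommon and sharing limited. Each carer must claim the primary role, and the Background says that this role typically falls on one close and accessible relative. Both must also live in the study area. The interventions consist of a taught session, 28 days of logged practice and weekly contact, so seeing a relative's card or brochure is not the same as receiving them. Living apart makes sharing a device or daily workbook harder, and a household rule does cover the easiest route. Participants are asked to refer people like themselves, which need not mean relatives.

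Much of this stands, and it is why the table shows ceilings. It does not close the gap. The primary role is self-declared, and exclusion 3 would be unnecessary if that criterion already ensured one carer per family.

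Three stronger readings are tempting and unsupported:
- A reader might infer that a tenth or more of the sample is paired. The documents give no share at all.
- A reader might infer that correlated relatives undermine the precision of both aims. For Aim 1 the effect is negligible, and for Aim 2 it is small.
- A reader might infer that the gap affects only care partners and caretakers and so distorts the comparison of phases. In-home carers living apart can pass as well, and nothing shows how pairs would be spread over the phases.

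**Conclusion.** The point holds as a gap in the wording of a stated rule. Exclusion 3 does not secure one carer per care recipient, and neither screening, allocation nor analysis makes up for it. The consequence that matters is dilution of Aim 1 through content reaching control carers. On the assumptions shown, the worst case takes power from 80% to about 79%, 77% or 74% for 2%, 5% or 10% of carers in pairs; partial uptake would cost less. For Aim 2 the design effect is at most about 1.05 with up to 10% of carers in pairs and an ICC up to 0.5. The true size is unknown and probably small. The case for a change rests on its low cost and on the fact that contamination cannot be traced later without family links.

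**What to change.** Replace exclusion 3 with: *Another carer of the same care recipient (living or deceased) is already enrolled, whatever household they live in.*

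At telephone screening, ask who else in the family cares or cared for this relative. Staff then check those names against the Screening & Enrollment Log, which already holds participants' names (Additional Information). This moves the check from the candidate's knowledge of enrolments to the study's own records. Staff should not disclose who is enrolled. No identifier for the care recipient is needed. A relative whom the candidate does not name could still be missed.

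For carers already enrolled, record a family-link flag. This must be done before the log's identifiers are destroyed, which the confidentiality section schedules for after data collection. Then run a sensitivity analysis that keeps only the first-enrolled carer per care recipient. That removes the double counting. It does not undo contamination of a carer who is kept, but the flag shows how many pairs were split between an active arm and control.

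The cost is one reworded criterion, one screening question with a log check, one extra data field and one sensitivity analysis. A few second relatives become ineligible, and screening takes slightly longer.
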